### **Collection of Pregnancy Information from Female Participants Who Become Pregnant**

- The investigator will collect pregnancy information on any female participant who becomes pregnant while participating in this study. The initial information will be recorded on the PPD paper pregnancy report form and faxed to the same fax number as may be used for backup SAE reports within 24 hours of learning of a participant's pregnancy.
- The participant will be followed to determine the outcome of the pregnancy. The investigator will collect follow-up information on the participant and the neonate, and the information will be forwarded to the sponsor. Generally, follow-up will not be required for longer than 6 to 8 weeks beyond the estimated delivery date. Any termination of pregnancy will be reported, regardless of fetal status (presence or absence of anomalies) or indication for the procedure.

- While pregnancy itself is not considered to be an AE or SAE, any pregnancy complication or elective termination of a pregnancy for medical reasons will be reported as an AE or SAE.
- A spontaneous abortion (occurring at <22 weeks gestational age) or still birth (occurring at >22 weeks gestational age) is always considered to be an SAE and will be reported as such.
- Any poststudy pregnancy-related SAE considered reasonably related to the IP by the investigator will be reported to the sponsor as described in [Section 6.1.1.3](#). While the investigator is not obligated to actively seek this information in former study participants, he or she may learn of an SAE through spontaneous reporting.
- Any female participant who becomes pregnant while participating in the study will discontinue the IP.

### 13.3 Appendix 3: Bayesian Logistic Regression Model

A Bayesian logistic regression model will be used to determine posterior probabilities of unacceptable reactogenicity (Grade 3 solicited AEs) at the current or next dose level in Part A, as described below:

$$\text{logit}(p(d)) = (\alpha + \beta_1 * \log(d/d^*)) + \beta_2 (\text{indicator of OA})$$

where

- $p(d)$  represents the probability of having a Grade 3 event at dose  $d$ ,
- $\text{logit}(p) = \ln(p/(1-p))$ ,
- $d^* = 50 \mu\text{g}$  is the reference dose,
- $\alpha$  is an intercept parameter, reflecting the expected logit value at the  $50 \mu\text{g}$  reference dose level,
- $\beta_1$  is a dose effect,
- $\beta_2$  is an age group effect.

The prior for  $\alpha$  and  $\ln(\beta_1)$  is a mixture of 2 bivariate normal distributions:

1. 80% weight for  $\alpha \approx \text{normal}(\text{mean}=-0.8473, \text{var}=1)$  and  $\ln(\beta_1) \approx \text{normal}(\text{mean}=-0.0556, \text{var}=1)$ , reflecting a rate of 30% at  $50 \mu\text{g}$ , and 10% at  $12 \mu\text{g}$ .
2. 20% weight for  $\alpha \approx \text{normal}(\text{mean}=-0.4055, \text{var}=1)$  and  $\ln(\beta_1) \approx \text{normal}(\text{mean}=0.10612, \text{var}=1)$ , reflecting an intolerable dose (ie, a rate of 40% at  $50 \mu\text{g}$  and 12% at  $12 \mu\text{g}$ ).

The prior  $\beta_2$  is half normal ( $\text{mean}=0$ ,  $\text{variance}=0.25$ ,  $\beta_2 < 0$  to reflect lower reactogenicity in older age group [OA]).

The covariance between priors is assumed to be zero.

A greater than 50% posterior probability that the rate at a current or next dose is greater than 30% will inform the SRT in their decision to continue at the current or next dose. This will be applied by each dose and age group.

Hypothetical scenarios for determining posterior probabilities based on combined younger age group and older age group data are presented in [Table 13-2](#).

**Table 13-2 Hypothetical Data Scenarios for Determining Posterior Probabilities**

Scenario	Dose (μg)	#Events	#Participants	CD – P(OD)	Next Dose	ND – P(TD)	ND – P(OD)
1	12	0	30	0	25	0.984	0.016
	25	0	30	0	50	0.860	0.1442
	50	0	30	0	100	0.917	0.083
	100	0	30	0	200	0.984	0.016
	200	0	30	0	-	-	-
2	12	0	30	-	25	0.984	0.016
	25	4	30	0.01	50	0.633	0.367
	50	6	30	0.097	100	0.352	0.648*
	100	8	30	0.407	200	0.1717	0.829*
	200	15	30	0.992*	-	-	-

\*Stopping rule met, ie,  $ND - P(OD) > 0.5$

CD = current dose; NA = not applicable; ND = next dose; P(TD) = probability of target dose; and P(OD) = probability of overdose.

In this evaluation, the age effect was not considered in the model.

When fitting the model, 0 events (#events) are replaced by 1 event (ie, assume 1 event in the younger adult group); this is done to prevent results from being overinfluenced by rates of events (=0%) being on the boundary of the parameter space. Rows in red should not be in the table, since the stopping rule would have been met at the previous dose; however, the rows are included for illustration purposes only.

**NOTE: It should be noted that the Bayesian model may be applied in a small number of exposed participants since it will be applied at each SRT review.**

## 13.4 Appendix 4: Potential Immune-mediated Diseases

Potential immune-mediated diseases are a subset of AEs that include autoimmune diseases and other inflammatory and/or neurologic disorders of interest which may or may not have an autoimmune etiology. Adverse events that need to be recorded and reported as pIMDs include those listed in [Table 13-3](#).

However, the investigator will exercise their medical and scientific judgment in deciding whether other diseases have an autoimmune origin (that is pathophysiologically involving systemic or organ-specific pathogenic autoantibodies) and should also be recorded as a pIMD.

When there is enough evidence to make any of the diagnoses mentioned in [Table 13-3](#), the AE must be reported as a pIMD. Symptoms, signs, or conditions which might (or might not) represent the above diagnoses, should be recorded and reported as AEs but not as pIMDs until the final or definitive diagnosis has been determined, and alternative diagnoses have been eliminated or shown to be less likely.

In order to facilitate the documentation of pIMDs in the eCRF, a pIMD standard questionnaire will be available to investigators.

Once a pIMD is diagnosed (serious or nonserious) in a study participant, the investigator (or designate) must complete, date, and sign an electronic Expedited Adverse Events Report.

**Table 13-3 List of Potential Immune-Mediated Diseases**

Medical Concept	Additional Notes
Blood disorders and coagulopathies	
Antiphospholipid syndrome	
Autoimmune aplastic anemia	
Autoimmune hemolytic anemia	
 
Includes warm antibody hemolytic anemia and cold antibody hemolytic anemia
 

Autoimmune lymphoproliferative syndrome (ALPS)	
Autoimmune neutropenia	
Autoimmune pancytopenia	

Medical Concept	Additional Notes
Autoimmune thrombocytopenia	
 
Frequently used related terms include: “autoimmune thrombocytopenic purpura”, “idiopathic thrombocytopenic purpura (ITP)”, “idiopathic immune thrombocytopenia”, “primary immune thrombocytopenia”.
 

Evans syndrome	
Pernicious anemia	
Thrombosis with thrombocytopenia syndrome (TTS)	
Thrombotic thrombocytopenic purpura	
 
Also known as “Moschcowitz-syndrome” or “microangiopathic hemolytic anemia”
 

Cardio-pulmonary inflammatory disorders	
Idiopathic Myocarditis/Pericarditis	Including but not limited to: 
 
Autoimmune / Immune-mediated myocarditis
 
Autoimmune / Immune-mediated pericarditis
 
Giant cell myocarditis
 

Idiopathic pulmonary fibrosis	Including but not limited to: 
 
Idiopathic interstitial pneumonia (frequently used related terms include “Interstitial lung disease”, “Pulmonary fibrosis”, “Immune-mediated pneumonitis”)
 
Pleuroparenchymal fibroelastosis (PPFE)
 

Pulmonary alveolar proteinosis (PAP)	
 
Frequently used related terms include: “pulmonary alveolar lipoproteinosis”, “phospholipidosis”
 

Endocrine disorders	
Addison’s disease	
Autoimmune / Immune-mediated thyroiditis	Including but not limited to: 
 
Hashimoto thyroiditis (autoimmune hypothyroidism, lymphocytic thyroiditis)
 
Atrophic thyroiditis
 
Silent thyroiditis
 
Thyrotoxicosis
 

Autoimmune diseases of the testis and ovary	
 
Includes autoimmune oophoritis, autoimmune ovarian failure and autoimmune orchitis
 

Autoimmune hyperlipidemia	
Autoimmune hypophysitis	
Diabetes mellitus type I	

Medical Concept	Additional Notes
Grave's or Basedow's disease	
 
Includes Marine Lenhart syndrome and Graves' ophthalmopathy, also known as thyroid eye disease (TED) or endocrine ophthalmopathy
 

Insulin autoimmune syndrome	
Polyglandular autoimmune syndrome	
 
Includes Polyglandular autoimmune syndrome type I, II, and III
 

Eye disorders	
Ocular Autoimmune / Immune-mediated disorders	
Including but not limited to:
 
 
Acute macular neuroretinopathy (also known as acute macular outer retinopathy)
 
Autoimmune / Immune-mediated retinopathy
 
Autoimmune / Immune-mediated uveitis, including idiopathic uveitis and sympathetic ophthalmia
 
Cogan's syndrome: an oculo-audiovestibular disease
 
Ocular pemphigoid
 
Ulcerative keratitis
 
Vogt-Koyanagi-Harada disease
 

Gastrointestinal disorders	
Autoimmune / Immune-mediated pancreatitis	
Celiac disease	
Inflammatory Bowel disease	
Including but not limited to:
 
 
Crohn's disease
 
Microscopic colitis
 
Terminal ileitis
 
Ulcerative colitis
 
Ulcerative proctitis
 

Hepatobiliary disorders	
Autoimmune cholangitis	
Autoimmune hepatitis	
Primary biliary cirrhosis	
Primary sclerosing cholangitis	
Musculoskeletal and connective tissue disorders	
Gout	
 
Includes gouty arthritis
 

Medical Concept	Additional Notes
Idiopathic inflammatory myopathies	
Including but not limited to:
 
 
• Dermatomyositis
 
• Inclusion body myositis
 
• Immune-mediated necrotizing myopathy
 
• Polymyositis
 

Mixed connective tissue disorder	
Polymyalgia rheumatica (PMR)	
Psoriatic arthritis (PsA)	
Relapsing polychondritis	
Rheumatoid arthritis	
Including but not limited to:
 
 
• Rheumatoid arthritis-associated conditions
 
• Juvenile idiopathic arthritis
 
• Palindromic rheumatism
 
• Still's disease
 
• Felty's syndrome
 

Sjögren's syndrome	
Spondyloarthritis	
Including but not limited to:
 
 
• Ankylosing spondylitis
 
• Juvenile spondyloarthritis
 
• Kera toderma blenorragica
 
• Psoriatic spondylitis
 
• Reactive Arthritis (Reiter's Syndrome)
 
• Undifferentiated spondyloarthritis
 

Systemic lupus erythematosus	
 
• Includes Lupus associated-conditions (eg, Cutaneous lupus erythematosus, Lupus nephritis) or complications such as shrinking lung syndrome (SLS)
 

Systemic scleroderma (systemic sclerosis)	
 
• Includes Reynolds syndrome (RS), systemic sclerosis with diffuse scleroderma and systemic sclerosis with limited scleroderma (also known as CREST syndrome)
 

Neuroinflammatory/neuromuscular disorders	
Acute disseminated encephalomyelitis (ADEM) and	
Includes the following:
 
 
• Acute necrotizing myelitis
 

Medical Concept	Additional Notes
other inflammatory demyelinating variants	
 
• Bickerstaff's brainstem encephalitis
 
• Disseminated necrotizing leukoencephalopathy (also known as Weston-Hurst syndrome, acute hemorrhagic leuko-encephalitis, or acute necrotizing hemorrhagic encephalomyelitis)
 
• Myelin oligodendrocyte glycoprotein antibody-associated disease
 
• Neuromyelitis optica (also known as Devic's disease)
 
• Noninfective encephalitis / encephalomyelitis / myelitis
 
• Postimmunization encephalomyelitis
 

Guillain-Barré syndrome (GBS)	
 
• Includes variants such as Miller Fisher syndrome and the acute motor and sensory axonal neuropathy (AMSAN)
 

Idiopathic cranial nerve palsies/paresis and inflammations (neuritis)	
Including but not limited to:
 
 
• Cranial nerve neuritis (eg, optic neuritis)
 
• Idiopathic nerve palsies/paresis (eg, Bell's palsy)
 
• Melkersson-Rosenthal syndrome
 
• Multiple cranial nerve palsies/paresis
 

Multiple sclerosis (MS)	
Includes the following:
 
 
• Clinically isolated syndrome (CIS)
 
• Malignant MS (the Marburg type of MS)
 
• Primary-progressive MS (PPMS)
 
• Radiologically isolated syndrome (RIS)
 
• Relapsing-remitting MS (RRMS)
 
• Secondary-progressive MS (SPMS)
 
• Uhthoff's phenomenon
 

Myasthenia gravis	
 
• Includes ocular myasthenia and Lambert-Eaton myasthenic syndrome
 

Narcolepsy	
 
• Includes narcolepsy with or without presence of unambiguous cataplexy
 

Peripheral inflammatory demyelinating neuropathies and plexopathies	
Including but not limited to:
 
 
• Acute Brachial Radiculitis (also known as Parsonage-Turner Syndrome or neuralgic amyotrophy)
 
• Antibody-mediated demyelinating neuropathy
 
• Chronic idiopathic axonal polyneuropathy (CIAP)
 
• Chronic Inflammatory Demyelinating Polyradiculoneuropathy (CIDP), including atypical CIDP variants (eg, multifocal acquired
 

Medical Concept	Additional Notes
	
demyelinating sensory and motor neuropathy also known as Lewis-Sumner syndrome)
 
 
• Multifocal motor neuropathy (MMN)
 

Transverse myelitis (TM)	
 
• Includes acute partial transverse myelitis (APTM) and acute complete transverse myelitis (ACTM)
 

Renal disorders	
Autoimmune / Immune-mediated glomerulonephritis	
Including but not limited to:
 
 
• IgA nephropathy
 
• IgM nephropathy
 
• C1q nephropathy
 
• Fibrillary glomerulonephritis
 
• Glomerulonephritis rapidly progressive
 
• Membranoproliferative glomerulonephritis
 
• Membranous glomerulonephritis
 
• Mesangioproliferative glomerulonephritis
 
• Tubulointerstitial nephritis and uveitis syndrome
 

Skin and subcutaneous tissue disorders	
Alopecia areata	
Autoimmune / Immune-mediated blistering dermatoses	
Including but not limited to:
 
 
• Bullous Dermatitis
 
• Bullous Pemphigoid
 
• Dermatitis herpetiformis
 
• Epidermolysis bullosa acquisita (EBA)
 
• Linear IgA-mediated bullous dermatosis (LABD), also known as Linear IgA disease
 
• Pemphigus
 

Erythema multiforme	
Erythema nodosum	
Reactive granulomatous dermatitis	
Including but not limited to
 
 
• Interstitial granulomatous dermatitis
 
• Palisaded neutrophilic granulomatous dermatitis
 

Lichen planus	
 
• Includes lichen planopilaris
 

Medical Concept	Additional Notes
Localized Scleroderma (Morphea)	
 
Includes Eosinophilic fasciitis (also called Shulman syndrome)
 

Psoriasis	
Pyoderma gangrenosum	
Stevens-Johnson Syndrome (SJS)	Including but not limited to: 
 
Toxic Epidermal Necrolysis (TEN)
 
SJS-TEN overlap
 

Sweet's syndrome	
 
Includes Acute febrile neutrophilic dermatosis
 

Vitiligo	
Vasculitis	
Large vessels vasculitis	Including but not limited to: 
 
Arteritic anterior ischemic optic neuropathy (AAION or arteritic AION)
 
Giant cell arteritis (also called temporal arteritis)
 
Takayasu's arteritis
 

Medium sized and/or small vessels vasculitis	Including but not limited to: 
 
Anti-neutrophil cytoplasmic antibody (ANCA) positive vasculitis (type unspecified)
 
Behcet's syndrome
 
Buerger's disease (thromboangiitis obliterans)
 
Churg–Strauss syndrome (a allergic granulomatous angiitis)
 
Erythema induratum (also known as nodular vasculitis)
 
Henoch-Schonlein purpura (also known as IgA vasculitis)
 
Microscopic polyangiitis
 
Necrotizing vasculitis
 
Polyarteritis nodosa
 
Single organ cutaneous vasculitis, including leukocytoclastic vasculitis, hypersensitivity vasculitis and acute hemorrhagic edema of infancy (AHEI)
 
Wegener's granulomatosis
 

Other (including multisystemic)	
Anti-synthetase syndrome	
Capillary leak syndrome	
 
Frequently used related terms include: "systemic capillary leak syndrome (SCLS)" or "Clarkson's Syndrome"
 

Medical Concept	Additional Notes
Goodpasture syndrome	
 
Frequently used related terms include: “pulmonary renal syndrome” and “anti-Glomerular Basement Membrane disease (anti-GBM disease)”
 

Immune-mediated enhancement of disease	
 
Includes vaccine-associated enhanced disease (VAED and VAERD). Frequently used related terms include “vaccine-mediated enhanced disease (VMED)”, “enhanced respiratory disease (ERD)”, “vaccine-induced enhancement of infection”, “disease enhancement”, “immune enhancement”, and “antibody-dependent enhancement (ADE)”
 

Immunoglobulin G4 related disease	
Langerhans' cell histiocytosis	
Multisystem inflammatory syndromes	
Including but not limited to:
 
 
Kawasaki's disease
 
Multisystem inflammatory syndrome in adults (MIS-A)
 
Multisystem inflammatory syndrome in children (MIS-C)
 

Overlap syndrome	
Raynaud's phenomenon	
Sarcoidosis	
 
Includes Löfgren syndrome
 

Susac's syndrome	

### **13.5 Appendix 5: Grading for Laboratory Abnormalities**

Laboratory abnormalities will be graded for severity using the following FDA toxicity grading table ([DHHS 2007](#)). Clinically relevant laboratory abnormalities (Grades 1-3) will be reported as AEs. All Grade 4 laboratory abnormalities will be reported as SAEs.

**Table 13-4      Toxicity Grading for Serum Laboratory Abnormalities**

Parameter	Mild (Grade 1)	Moderate (Grade 2)	Severe (Grade 3)	Potentially Life-Threatening (Grade 4)
Hematology (Whole Blood)				
Hemoglobin (g/dL) - Female	11.0 – 12.0	9.5 – 10.9	8.0 – 9.4	<8.0
Hemoglobin (g/dL) – Female Change from Baseline Value	Any decrease – 1.5	1.6 – 2.0	2.1 – 5.0	>5.0
Hemoglobin (g/dL) - Male	12.5 – 13.5	10.5 – 12.4	8.5 – 10.4	<8.5
Hemoglobin (g/dL) - Male Change from Baseline Value	Any decrease – 1.5	1.6 – 2.0	2.1 – 5.0	>5.0
Platelets Decrease (cell/mm  )	125,000 – 140,000	100,000 – 124,000	25,000 – 99,000	<25,000
WBC Increase (cell/mm  )	10,800 – 15,000	15,001 – 20,000	20,001 – 25,000	>25,000
WBC Decrease (cell/mm  )	2500 – 3500	1500 – 2499	1000 – 1499	<1000
Lymphocytes Decrease (cell/mm  )	750 – 1000	500 – 749	250 – 499	<250
Neutrophils Decrease (cell/mm  )	1500 – 2000	1000 – 1499	500 – 999	<500
Eosinophils (cell/mm  )	650 – 1500	1501 – 5000	>5000	Hypereosinophilic
Biochemistry (Serum)				
Alkaline phosphatase (increase by factor)	1.1 – 2.0 x ULN	2.1 – 3.0 x ULN	3.1 – 10 x ULN	> 10 x ULN
ALT (increase by factor)	1.1 – 2.5 x ULN	2.6 – 5.0 x ULN	5.1 – 10 x ULN	>10.0 x ULN
AST (increase by factor)	1.1 – 2.5 x ULN	2.6 – 5.0 x ULN	5.1 – 10 x ULN	>10.0 x ULN
Bilirubin – when accompanied by any increase in Liver Function Test (increase by factor)	1.1 – 1.25 x ULN	1.26 – 1.5 x ULN	1.51-1.75 x ULN	> 1.75 x ULN
Bilirubin – when Liver Function Test is normal (increase by factor)	1.1 – 1.5 x ULN	1.6 – 2.0 x ULN	2.0 – 3.0 x ULN	> 3.0 x ULN
BUN (mg/dL)	23 – 26	27 – 31	>31	Requires dialysis
Creatinine (mg/dL)	1.5 – 1.7	1.8 – 2.0	2.1 – 2.5	>2.5 or requires dialysis

ALT = alanine aminotransferase; AST = aspartate aminotransferase; BUN = blood urea nitrogen; ULN = upper limit of the normal range; WBC = white blood cells.

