All protocol-required laboratory assessments must be conducted in accordance with the Laboratory Manual. If laboratory values from non-protocol-specified laboratory assessments performed at the local study site laboratory require a change in participant management or are considered clinically significant by the investigator, then the results must be recorded in the eCRF.

A maximum of 120 mL of blood will be collected per participant per visit. This may include ~~50~~ mL of blood collected at 3 visits for participants in Part A enrolled at sites [REDACTED] [REDACTED] The maximum amount of blood collected over the 6-month duration of the study is approximately 500 mL. Repeat or unscheduled samples may be taken for safety reasons or for technical issues with the samples.

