### 7.5.2 Analysis of the Primary Safety Endpoints

The primary safety endpoints as detailed in [Section 2](#) will be analyzed as described in the SAP. Laboratory abnormalities will be graded for severity following the FDA toxicity grading table ([Section 13.5](#)). For all safety endpoints, descriptive summary statistics will be provided for the Safety Set. Safety data listings will also be provided.

Refer to [Section 13.3](#) for details on Bayesian logistic regression used during the safety monitoring of the study.

In addition to the planned summary of SAEs throughout the study, any SAEs that are reported will also be summarized within 28 days of study vaccine administration.

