2.1. Primary Objective and Endpoints

Objectives	Endpoints
Primary – Safety	
To evaluate the safety and tolerability of CV0501 at each dose level	
 Percentage of participants with each solicited local and systemic AEs during 7 days after vaccination (i.e., the day of study vaccination and 6 subsequent days (day 1 through 7) Percentage of participants with each abnormal clinical safety laboratory finding for 8 days after study vaccination Percentage of participants with unsolicited AEs for 28 days after study vaccination Percentage of participants with MAAEs, AESIs and SAEs from study vaccination through the end of the study (for 180 days after the study vaccine administration), each summarized separately

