3.4. Dose Adjustment/Modifications

An overdose is any dose of study vaccine given to a participant that exceeds the planned dose for an individual within a given dose group.

There is no specific treatment recommended for an overdose. Overdose itself is not to be reported as an adverse event (AE). Overdose participants will be included in the Safety Set and excluded from Per protocol Immunogenicity (PPI) Set.

4. General Statistical Considerations

Participants will be identified in the listings by the participant identification number concatenated with the site number. Data will be displayed in all listings sorted by age group, dose group and participant number.

Continuous data will be described using descriptive statistics (n, mean, standard deviation, median, minimum, and maximum).

Categorical data will be described using the participant count and percentage for each category.

For the **summary statistics** of all numerical variables unless otherwise specified, mean, confidence interval, median, standard deviation, minimum and maximum will be displayed.

A row denoted “Missing” will be included in count tabulations where specified on the shells to account for dropouts and missing values.

There is no formal hypothesis testing in this study where statistical methods are applied, the emphasis will be on estimation with 2-sided 95% Confidence intervals (CIs).

The denominator for all percentages will be the number of participants with non-missing values of corresponding parameter in that treatment within the analysis population of interest, unless otherwise specified.

A table, figure, listing (TLF) is to be generated for any required item even where no data is available or reported. In such cases, the table, figure or listing will state: “**No Data Reported**”. This will confirm to the health authorities that all data for the tables, figures, listings, and narratives are accounted for.

Baseline will be defined as the last non-missing evaluation prior to study vaccine administration, unless otherwise specified.

Study day will be calculated as follows:

- study day prior to the injection will be calculated as: date of assessment – date of the injection
- study day on or after the date of the injection will be calculated as: date of assessment – date of the injection + 1

For Safety assessment of AEs, the intervals will be calculated as follow

- solicited AEs: the day of vaccination and 6 subsequent days (day 1 through 7)

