9.2 Clinical Laboratory Evaluations

The following laboratory assessments will be performed:

Hematology:	Basophils, eosinophils, erythrocytes (red blood cells), hemoglobin, leukocytes (white blood cells), lymphocytes, monocytes, neutrophils, and platelets
Chemistry:	Alanine aminotransferase, alkaline phosphatase, aspartate aminotransferase, total and direct bilirubin, blood urea nitrogen, and creatinine
SARS-CoV-2:	
 SARS-CoV-2 serology (antibody) will include N protein for prevaccination and postvaccination timepoints. SARS-CoV-2 RT-PCR (nasopharyngeal or mid-turbinate swab)
HIV/HBV/HCV	
 Hepatitis B surface antigen test HIV 4th generation antigen/Ab test Anti-HCV Ab test (and RNA test if anti-HCV Ab positive)
Other analyses:	
Female participants of childbearing potential:
 
 β-human chorionic gonadotropin (serum test at screening; urine test at additional time points) Serum FSH, to confirm postmenopausal status

Individual safety laboratory measurements for hematology, chemistry and coagulation laboratory panel will be provided. All listings will include the cohort, study vaccine, participants ID, laboratory test name result, date and time of measurements, reference range, and flag for measurements that are outside the reference range and sorted by age group, dose group and participant number.

Laboratory abnormalities will be graded for severity using the FDA toxicity grading table (DHHS 2007). Clinically relevant laboratory abnormalities will be reported as AEs using the AE grading.

A summary of patients with an abnormal laboratory value after study vacation (up to Day 8) will be presented. An abnormal laboratory is defined as any value outside of the normal range.

A by-participant listing will be provided for pregnancy test by age group, dose group and participant number.

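### SAP 9.2 counts only out-of-range laboratory values as abnormal, so a hemoglobin fall that Table 13-4 grades 2 or 3 is missing from the primary laboratory percentage if it stays in range

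*Protocol*

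**What the plan says.** SAP 2.1 lists this primary endpoint: "Percentage of participants with each abnormal clinical safety laboratory finding for 8 days after study vaccination".

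Protocol 7.5.2, on the primary safety endpoints, says: "Laboratory abnormalities will be graded for severity following the FDA toxicity grading table". The table is Table 13-4 in Appendix 5. For each sex it gives two hemoglobin scales:

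- **Absolute value.** Grade 1 is 12.5-13.5 g/dL in men and 11.0-12.0 g/dL in women.
- **Change from baseline, same cut-offs for both sexes.** Grade 1 is "Any decrease – 1.5" g/dL, Grade 2 is 1.6-2.0, Grade 3 is 2.1-5.0 and Grade 4 is above 5.0.

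SAP 9.2 also names the FDA table for grading, but then sets the rule for its one planned laboratory summary, which runs to Day 8: "An abnormal laboratory is defined as any value outside of the normal range". The listings flag values outside the reference range. SAP section 4 sets the baseline: "Baseline will be defined as the last non-missing evaluation prior to study vaccine administration, unless otherwise specified". Hematology is scheduled at screening, on Day 1 before dosing, and on Day 8.

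**The concern.** The protocol's grading table treats a large fall from a participant's own baseline as Grade 2 or 3 wherever the later value lands. The SAP's definition of abnormal looks only at where the value lands. Neither document says what happens when the two disagree, and SAP section 13 does not list the definition as a change from the protocol.

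If SAP 9.2 is followed as written, a participant with a Grade 3 fall on the trial's own table is counted as normal in a primary safety percentage. No other planned laboratory table would reveal it: SAP 9.2 describes no tabulation by grade and no change-from-baseline summary. Vital signs, by contrast, get change-from-baseline summaries in SAP 9.3. Most baselines should be in range, since exclusion criterion 8 keeps out new, clinically significant screening abnormalities of Grade 1 or higher. These are the participants in whom such a fall can go uncounted.

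**Working it through.** The plan gives no figure for this point, so there is none to reproduce.

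**1. Worked cases.** The laboratory's reference range is not in the documents. As a stand-in for its lower limit I take the top of the absolute Grade 1 band, 13.5 g/dL (men) and 12.0 g/dL (women).

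- Man, 16.0 to 13.8: fall 2.2, Grade 3 on change; 13.8 > 13.5, so not abnormal under SAP 9.2.
- Woman, 14.2 to 12.1: fall 2.1, Grade 3; 12.1 > 12.0, not abnormal.
- Man, 15.2 to 13.6: fall 1.6, Grade 2; not abnormal.
- Woman, 13.7 to 12.1: fall 1.6, Grade 2; not abnormal.

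**2. Share of such falls that stay in range.** Let baseline be normal with mean m and SD s, lower limit L and fall f. Given an in-range baseline,

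share = [1 − Φ((L + f − m)/s)] / [1 − Φ((L − m)/s)].

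Assumed, not in the documents: m = 15.0, s = 1.0 (men); m = 13.6, s = 0.9 (women).

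- Men, f = 1.6: [1 − Φ(0.10)] / [1 − Φ(−1.50)] = 0.460/0.933 = 0.49.
- Men, f = 2.1: [1 − Φ(0.60)] / 0.933 = 0.274/0.933 = 0.29.
- Women, f = 1.6: [1 − Φ(0)] / [1 − Φ(−1.78)] = 0.500/0.962 = 0.52.
- Women, f = 2.1: [1 − Φ(0.56)] / 0.962 = 0.289/0.962 = 0.30.

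These shares are conditional on a fall of that size having occurred. They do not say how often one will. A lower laboratory limit would raise them and a higher one would reduce them.

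**3. Where to cut: the Grade 1 change row.** Assume no vaccine effect, within-person SD w = 0.3 to 0.5 g/dL (not in the documents) and results to 0.1 g/dL. Then P(any decrease) = Φ(−0.05/(√2·w)):

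- w = 0.3: 0.453
- w = 0.4: 0.465
- w = 0.5: 0.472

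That is 30 × 0.453 = 13.6 to 30 × 0.472 = 14.2 participants in a cohort of 30. A rule that made any decrease abnormal would be mostly noise.

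**4. Where to cut: a fall of 1.6 g/dL or more.** On the same basis, P(chance fall) = Φ(−1.55/(√2·w)) = 0.0001, 0.003 and 0.014 for w = 0.3, 0.4 and 0.5.

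For an upper bound, add blood sampling. Protocol 6.1.4 says: "A maximum of 120 mL of blood will be collected per participant per visit". With an assumed blood volume of 5 L and hemoglobin of 14 g/dL, 120/5,000 × 14 = 0.34 g/dL. At w = 0.5 this gives Φ(−(1.55 − 0.34)/0.707) = Φ(−1.71) = about 0.04. It assumes everyone gives the maximum and none recovers by Day 8.

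A simulation restricted to in-range baselines (population mean 15.0 for men and 13.5 for women, SD 0.9; w from 0.2 to 0.6) counted only falls of 1.6 or more that ended in range, which are the ones a new rule would add. They occurred in 0 to 2.6% of participants with no mean drop, and in 0 to 4.0% with an assumed mean drop of 0.2 g/dL. The Grade 2 cut therefore carries little noise.

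**The case against.** Several points on the other side are sound.

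- **The texts can be read together.** The documents say that abnormalities will be graded, so grading could apply only to values already out of range. On that reading there is no contradiction, but the change rows then do nothing for an in-range value, and neither document says that this is intended.
- **Falls are not lost to safety review.** Protocol 6.1 has abnormal results, including those that worsen from baseline, recorded as AEs. Protocol 6.1.4 has clinically relevant changes recorded. Appendix 5 says: "Clinically relevant laboratory abnormalities (Grades 1-3) will be reported as AEs". Holding rule 2a includes clinically relevant laboratory abnormalities, individual values are listed, and unsolicited AEs are themselves a primary endpoint. This stands, and it limits the point to the laboratory percentage. It does not close the gap. In practice the AE route turns largely on the investigator's judgment of relevance, and protocol 6.1.4 and SAP 9.2 grade such AEs on the AE intensity scale, so a symptomless Table 13-4 Grade 3 fall could appear as a mild AE.
- **The consequence is modest.** There is no hypothesis testing, and the dose-escalation model uses Grade 3 solicited AEs, not laboratory values. Nothing in the documents suggests that the vaccine lowers hemoglobin.

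A reader might also infer that the plan labels about half of unaffected participants abnormal. It does not. SAP 9.2 holds the only definition of abnormal, and under it an in-range hemoglobin is never abnormal. The 45-47% would arise only if every value were graded and Grade 1 were then read as abnormal, which no section states. Nor is the Grade 1 change row an error: the protocol presents it as part of the FDA scale. A high background rate for that row would blur a dose gradient without making it undetectable.

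**Conclusion.** The point holds for the laboratory endpoint. SAP 9.2, followed as written, counts as normal a hemoglobin fall that Table 13-4 grades 2 or 3 whenever the later value is in range, and no planned laboratory summary would show it. This follows from the text; only the exact values in the worked cases depend on the stand-in limits of 13.5 and 12.0 g/dL.

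Its size is conditional: about half of 1.6 g/dL falls and about 30% of 2.1 g/dL falls from an in-range baseline would go uncounted, given the stand-in limits and the assumed baseline distributions. How often such falls will occur cannot be estimated from the documents. Chance alone produces few, so what is at stake is a real fall, should one occur, being missing from the by-dose percentage. It is worth correcting because the remedy is cheap. It does not threaten the trial's safety oversight or its escalation decisions.

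**What to change.** In SAP 9.2, count hemoglobin as abnormal if the value is outside the normal range **or** has fallen from the pre-dose baseline by Grade 2 or more on Table 13-4 (at least 1.6 g/dL), even when the later value is in range. Show the change-based Grade 2 or higher count on its own line by dose group, so that readers can separate the two routes. State that the Grade 1 change row alone does not make a participant abnormal; the noise calculation is the reason for that cut-off. Record the definition in SAP section 13.

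The cost is SAP wording and one derived variable from Day 1 and Day 8 hemoglobin, which are already collected. No visit, sample or clinical rule changes. The downside is that the hemoglobin percentage may rise slightly: chance falls of this size that end in range would add about 0 to 4% of participants under the assumptions tried, at most 30 × 0.04 = 1.2 participants per cohort of 30.
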